---

## 1. General information

### 1.1 Title of the project

Project Meaningful Activities and Recovery (MA&R)

### 1.2 Trial registration number

ClinicalTrials.gov NCT03963245.

### 1.3 SAP version number

This is a detailed version of the SAP description in the protocol (Danish latest version 5 sent to Regional Ethics Committee e) and protocol paper ([name] *et al.*, 2020). This detailed SAP is version 1, July 2021. The headings in this SAP are in many instances aligned with the structure recommended by Gamble *et al.* (Gamble *et al.*, 2017).

## 2. Introduction

### 2.1 Trial background and rationale

The background and rationale are described detailed in the protocol paper ([name] *et al.*, 2020).

### 2.2 Objectives or hypotheses

From the protocol paper ([name] *et al.*, 2020):

“The primary objective of this RCT is to determine whether MA&R in addition to standard mental healthcare is more effective than standard mental healthcare alone regarding activity engagement (POES-S) [38, 39] in a sample of individuals living with psychiatric disabilities. The intervention is being tested in addition to standard mental healthcare as it is an add-on to usual care. The second objective of this study is to evaluate whether MA&R in addition to standard mental healthcare is more effective than standard mental healthcare alone regarding outcomes related to activity engagement, e.g. functioning, personal recovery and quality of life”

### 3. Study Methods

#### 3.1 Trial design

A multicenter two arm, parallel randomized controlled trial. Eligible participants were individuals with psychiatric disabilities, who were treated in one of three community mental health centers in Mental Health Center Copenhagen, or were citizens in the municipalities of Copenhagen, Svendborg or Odense. Included participants were allocated with a 1:1 ratio to either Meaningful Activities and Recovery (MA&R) a novel rehabilitation intervention, in addition to usual care, or usual care alone. The enrollment started at September 2018 and lasted to August 2020. MA&R lasts for about eight months and consists of 11 group sessions and 11 one-to-one sessions.

From the protocol ([name] et al, 2020)

“MA&R is delivered by a peer worker and an Occupational therapist. In addition to the planned sessions, the participants are offered individualized support to engage in meaningful activities. The MA&R is a manualized intervention, with a workbook developed for the participants to support learning and personal exploration. MA&R utilized various methods such as didactic presentations, peer exchange, direct experiences with activities and personal exploration. The MA&R contains two courses: MA&R I and MA&R II which complement each other. In MA&R I, the participants can explore and identify meaningful activities, while MA&R II supports anchoring new activities and habits in everyday life.”

Data was collected twice, baseline before randomization and at follow up, at the end of the intervention.

#### 3.2 Randomization

From the protocol paper ([name], et al. 2020):

After baseline data are obtained, the participants are randomly assigned to either the control (standard mental healthcare) or experimental group (MA&R + standard mental healthcare) with a 1:1 allocation using the randomization module in REDCap (Research Electronic Data Capture) [44, 45]. The randomization sequence was generated by a researcher employed outside the research team and entered to RedCap. The randomization is stratified by sex. Varying block sizes, unknown to the research team, are used. To ensure concealment, the randomization schedule is stored away from the research team and the block sizes are not disclosed. The allocation is performed by the researcher, who informs the participants and the counsellors and who assigns participants to the interventions.”

Participants gave informed consent (verbal and written) and filled out the baseline questionnaire before randomization.

### 3.3 Sample size calculation

Below numbers are retrieved from the protocol paper ([name] et.al 2020).

- Type 1 error set at: 0.05 ( $\alpha$ )
- Power: 0.80 ( $\beta$ )
- Difference in mean: 3 points
- within group standard deviation (SD): 6

From the protocol paper ([name] *et al.*, 2020): “The sample size is calculated based on the primary hypothesis to detect a minimal but clinically significant difference between the intervention group and the control group on POES-S (increased engagement in meaningful activities). In a recent RCT testing, the intervention Balancing Everyday Life (BEL) in a similar population as that in this study, Eklund et al. found a small effect of 1.4 points measured on POES-S ( $d = 0.27$ ) [21]. As MA&R has a more comprehensive format (in terms of duration and costs) than BEL, the clinically significant difference between the study groups is set to 3 points, corresponding to a moderate effect size (Cohens  $d = 0.5$ ). Based on the BEL trial, we assume the standard deviation in the study population to be 6. To achieve a statistical power of 80% and a significance level of 5%, a total of 128 participants must be included in this study; 64 in each group to detect this difference.”

No interim analyses were planned.

There were no guidelines for stopping the trials early.

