### 3.5 Timing of outcome measurements

Post interventions, about 8 months: Questionnaires were sent out 1-7 days after the last one-on-one session. There is no definite upper limit for when the follow-up data is not relevant anymore; however, the contact procedure included 6 contact attempts for 3-8 weeks. Generally, data was considered not relevant after three months after the questionnaires were sent out. Exceptions from this rule was made, if participants were hospitalized at the time for follow up (and wanted to answer the questionnaires after discharge), or participants needed help for filling out questionnaires and had to wait until the end of the first COVID -19 lockdown before being offered assistance.

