## 4.2 Information to be included in the CONSORT flow diagram

Numbers of persons referred, screened for eligibility, fulfilled inclusion/exclusion criteria (excluded), followed up (answered questionnaires), loss to follow-up (did not want to answer questionnaire, never answered questionnaire), retracted consent, analyzed according to intention to treat (ITT) analyses.

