### 4.3.2 Withdrawal from research

It was always possible to drop out from research and thus not answer questionnaires at follow up. This was registered as e.g. *did not want to answer questionnaire/loss to follow-up* if the participant explicitly communicated this to the project, otherwise unspecified reason to dropout (e.g. *not possible to get in touch with participant/loss to follow-up*) was registered.

According to Danish law it is possible for participants to withdraw their consent and have all person sensitive data deleted. In these cases, data cannot be used in analyses. In these instances, we will keep the randomization result and projects specific ID (not identifiable CPR number) in the database. Dropout from research (loss to follow-up and withdrawn consent) is summarized at 8 months follow-up.

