# 5. Statistical principles and analysis

## 5.1. Confidence intervals and p-values

The two-sided significance level for statistical tests will be 5 %. Differences in means and proportions will be presented with a 95% confidence interval (CI) and a p-value. All primary, secondary and exploratory measures will be presented.

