### 5.5 Sensitivity analyses

No adjustments will be made in the primary analyses other than for stratification variables.

Sensitivity analyses are made with:

- Adjustment for baseline differences for those baseline characteristics with unequal/skewed baseline means and that can thus be associated with the outcome. Baseline characteristics in this case include (in addition to stratification variables) diagnosis, age, site and functioning) and self-reported outcome measures at baseline. Baseline tests will not be used exclusively in judging whether to include in the sensitivity analysis. Inclusion will be based on whether the groups are different to the extent that it could affect the analyses. The selection will be guided by CH.
- Imputations of missing values representing “worst” and “best” case of imputations. We will make two analyses: one where we in both groups replace imputations with “worst” case defined as the 90 percentiles from the imputed value and one where we in both groups replace imputations with “best” case defined as the 90 percentiles from the imputed value.
- The observed data.

Sensitivity analyses will be made for the primary outcome.

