## 5.9 Missing data

Multiple imputations will be used to address the issue of missing data. If possible, multiple multivariate normal regression imputations (Markov Chain Monte Carlo (MCMC)) will be used. This is possible if all imputed data follow the same distribution (e.g. are scale variables). A table of auxiliary variables are made based on the list of variables used in the MA&R project. These are chosen for being theoretically associated with the specific outcome. Also, variables that are predictive for missing data are included. This selection will be based on whether there is skewed dropout for the specific outcome variable. In the cases of extreme distributions predictive mean matching will be used instead of multivariate normal imputations. All variables in the model will also be included in the imputation model. We will perform at least 100 imputations for each analysis.

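### Section 3.3 gives 128 as the number to include for 80% power, but 64 per arm is the number that must supply the outcome, and the SAP plans for losses without restating the power

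*SAP*

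**What the plan says.** Section 3.3 takes its calculation from the protocol paper: a 3-point difference, SD 6, "Type 1 error set at: 0.05" and power 0.80. It concludes that "a total of 128 participants must be included in this study; 64 in each group to detect this difference". It mentions no attrition rate, no inflation, and no power for a smaller number of observed outcomes. Section 5.1 fixes the sidedness: "The two-sided significance level for statistical tests will be 5" per cent.

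Other sections of the SAP expect outcomes to be lost:

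- Section 4.2 puts in the flow diagram "loss to follow-up (did not want to answer questionnaire, never answered questionnaire), retracted consent".
- Section 3.5, on late questionnaires: "Generally, data was considered not relevant after three months after the questionnaires were sent out". It allows exceptions for hospitalisation and for people who needed help during the first lockdown.
- Section 4.3.2, on participants who withdraw consent and have their data deleted: "In these cases, data cannot be used in analyses".
- Section 5.9: "Multiple imputations will be used to address the issue of missing data".

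On the primary model, section 5.5 says: "No adjustments will be made in the primary analyses other than for stratification variables". Section 3.2 names one stratification variable, sex.

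**The concern.** A sample size from a two-sample comparison of means counts the participants whose outcome enters the comparison. Unless an allowance for loss is built in, the number to include has to be larger. Section 3.3 uses a single number for both, while other sections describe several ways in which an included participant may have no usable 8-month POES-S.

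If 128 people were included and some outcomes are missing, the trial does not have 80% power for 3 points on its own assumptions. No estimate is biased by this, and the 95% confidence interval promised in section 5.1 will show what a null result excludes. What would be wrong is the design claim printed beside it: a reader would credit the trial with a sensitivity to a 3-point effect that it may not have had.

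**Working it through.** **Inputs.** Difference 3, SD 6, alpha 0.05, power 0.80 (section 3.3); two-sided (section 5.1); 1:1 allocation (section 3.1). Standardised difference d = 3/6 = 0.5.

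**Step 1: reproduce the plan's figure.**

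- Normal approximation: n per arm = 2(1.960 + 0.842)² × 6²/3² = 62.8, rounded up to 63.
- Two-sample t-test (noncentral t, 2n − 2 degrees of freedom, noncentrality d√(n/2)): n = 63.77, rounded up to 64 per arm, 128 in total.

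The t-test gives the plan's number exactly with no losses, so it contains no hidden allowance. Power is 80.1% at 64 per arm (noncentrality 0.5√32 = 2.83) and 79.5% at 63. Adjusting for sex, with one degree of freedom fewer and no variance gain assumed, leaves 80.1% at 64.

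**Step 2: power when outcomes are lost.** The SAP gives no loss rate, so the rates below are assumptions. Observed n per arm = 64 × (1 − loss).

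| Assumed loss | Observed n per arm | Power for 3 points | Difference detectable at 80% |
|---|---|---|---|
| 0% | 64 | 80.1% | 2.99 |
| 5% | 60.8 | 78.1% | 3.07 |
| 10% | 57.6 | 75.8% | 3.16 |
| 20% | 51.2 | 70.7% | 3.35 |
| 30% | 44.8 | 64.8% | 3.59 |

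At 20% loss the chance of missing a true 3-point effect is 100 − 70.7 = 29.3%, against about 20% as planned.

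**Step 3: what multiple imputation gives back.** Suppose baseline POES-S is in the imputation model, its correlation with the 8-month score is ρ (an assumption), and outcomes are missing completely at random. The variance of an arm mean is then about SD²[(1 − ρ²)/n_obs + ρ²/64], so the effective size per arm is 1/[(1 − ρ²)/n_obs + ρ²/64].

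| ρ | Effective n, 20% loss | Power | Effective n, 30% loss | Power |
|---|---|---|---|---|
| 0.3 | 52.1 | 71.5% | 46.0 | 66.0% |
| 0.5 | 53.9 | 73.0% | 48.4 | 68.3% |
| 0.7 | 56.8 | 75.2% | 52.5 | 71.8% |

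A simulation (6000 trials, 100 imputations, Rubin's rules) gave 71.0, 72.2 and 75.3% at 20% loss and 65.4, 67.5 and 70.3% at 30%, for ρ = 0.3, 0.5 and 0.7. Imputation helps, but does not bring power back to 80%.

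**Step 4: possible reserves.**

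- *A smaller SD.* The earlier trial's 1.4 points and d = 0.27 quoted in section 3.3 imply SD = 1.4/0.27 = 5.2. With SD 5.2, power is 82.4% at 20% loss and 79.9% at 25%, so 80% would hold up to about 25% loss.
- *Baseline adjustment.* With POES-S at baseline as a covariate, residual variance falls by the factor 1 − ρ². At ρ = 0.5 and 51.2 observed per arm, power is 82.5%. A loss of 20% is offset once ρ² = 0.20, that is ρ of about 0.45.

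**The case against.** The strongest reply is that 128 is correct arithmetic and is quoted from the protocol paper, where an attrition allowance may stand outside the excerpt. The trial may also have enrolled more than 128: 128/0.80 = 160 would fully cover a 20% loss. Section 5.4 bases the analysis on everyone included, with imputation, so the word fits the nominal analysis set. Section 5.4.2 also quotes a repeated-measures mixed model that could draw strength from baseline POES-S, and the SD of 6 may be cautious. The SAP is dated July 2021 and enrolment ended in August 2020, so no recruitment decision depends on the restatement.

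Part of this stands. The actual loss and the actual enrolment are unknown, so nobody can say from the SAP how large the shortfall is, or that there was one. Section 3.5 is also looser than a strict cut-off: it sets no definite upper limit and lists exceptions.

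The rest does not remove the point. The SAP reproduces the calculation as its own statement of power, and the figure equals the zero-loss number. Keeping everyone in the analysis set preserves the count but not the information, and deleted data are excluded from the analyses altogether. The possible gain from a mixed model is not claimed in section 3.3. It also fits poorly with section 5.3, which defines the primary outcome as an end-point comparison, and with the limit on adjustment in section 5.5. The SAP adopts SD 6 and claims no reserve from a smaller value.

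**Conclusion.** The concern holds. The number 128 is right as the number of observed primary outcomes and wrong as the number to include, given the losses that the SAP itself provides for. If 128 were included, power for 3 points at SD 6 falls below 80% with the loss of even one outcome per arm. It is 75.8%, 70.7% and 64.8% at 10, 20 and 30% loss on complete cases, and about 71 to 75% at 20% loss and 65 to 72% at 30% with imputation.

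These sizes rest on assumed loss rates, an assumed correlation of 0.3 to 0.7, outcomes missing completely at random, and a primary analysis adjusted for sex only. A larger enrolment, an SD near 5.2 or baseline adjustment could close the gap, but the SAP states none of them as a reserve. The statement should be corrected; the validity of the treatment estimate is not in question.

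**What to change.** Do not enrol more. Add two sentences to section 3.3:

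> 80% power holds for 64 participants per arm with an observed 8-month POES-S. For the N expected to provide it, power for 3 points (SD 6) under the primary analysis, adjusted for sex only, is X%, and the difference detectable with 80% power is Y points.

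Set N from enrolment and response counts, without looking at outcomes by arm. If the number enrolled exceeded 128, the same sentences will show it. If adjustment for baseline POES-S is adopted as a separate change to the primary analysis, recompute X and Y under that model and state the assumed correlation.

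The cost is two sentences. Enrolment, data and analysis do not change; unless enrolment exceeded 128 by enough to cover the losses, the stated power becomes less favourable.

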### 3.5 Timing of outcome measurements

Post interventions, about 8 months: Questionnaires were sent out 1-7 days after the last one-on-one session. There is no definite upper limit for when the follow-up data is not relevant anymore; however, the contact procedure included 6 contact attempts for 3-8 weeks. Generally, data was considered not relevant after three months after the questionnaires were sent out. Exceptions from this rule was made, if participants were hospitalized at the time for follow up (and wanted to answer the questionnaires after discharge), or participants needed help for filling out questionnaires and had to wait until the end of the first COVID -19 lockdown before being offered assistance.

## 4. Trial population

### 4.1 Eligibility criteria

This is described detailed in the protocol paper ([name] et al, 2020).

## 4.2 Information to be included in the CONSORT flow diagram

Numbers of persons referred, screened for eligibility, fulfilled inclusion/exclusion criteria (excluded), followed up (answered questionnaires), loss to follow-up (did not want to answer questionnaire, never answered questionnaire), retracted consent, analyzed according to intention to treat (ITT) analyses.

## 4.3 Withdrawal

### 4.3.1 Withdrawal from treatment

It was always possible to drop out of treatment/intervention. Hereafter one could choose to participate in follow-up (answer questionnaire etc.) or not. If a person in the intervention group dropped out of treatment this was registered (+ preferably reason if possible). If the participant was in the control group drop out of treatment as usual was not registered as it was not possible to get this information.

### 4.3.2 Withdrawal from research

It was always possible to drop out from research and thus not answer questionnaires at follow up. This was registered as e.g. *did not want to answer questionnaire/loss to follow-up* if the participant explicitly communicated this to the project, otherwise unspecified reason to dropout (e.g. *not possible to get in touch with participant/loss to follow-up*) was registered.

According to Danish law it is possible for participants to withdraw their consent and have all person sensitive data deleted. In these cases, data cannot be used in analyses. In these instances, we will keep the randomization result and projects specific ID (not identifiable CPR number) in the database. Dropout from research (loss to follow-up and withdrawn consent) is summarized at 8 months follow-up.

## 4.4 Baseline characteristics

Sex, age, housing/marital status, educational level, diagnosis, work status, functional level (assessed by researcher). Register-based and self-reported baseline outcome measures will also be summarized.

# 5. Statistical principles and analysis

## 5.1. Confidence intervals and p-values

The two-sided significance level for statistical tests will be 5 %. Differences in means and proportions will be presented with a 95% confidence interval (CI) and a p-value. All primary, secondary and exploratory measures will be presented.

## 5.2 Adherence

Participant adherence to the MA&R is not defined as a minimum number of sessions that the participants have participated in. MA&R combines group sessions, individual sessions and individualized support. Participation

in group and one-on one session will be reported separately for the type of session and totally for the sessions together. Amount of individual support received measured in hours will be reported. MA&R is delivered in an individualized manner, which means that each MA&R course is tailored to each participant. Hence, the amount of support and session participated in, may vary extensively from participant to participant.

Fidelity to the MA&R intervention and its principles is evaluated through fidelity reports. Fidelity to MA&R will be described as a result of one or more fidelity reports (i.e. poor, good or excellent fidelity to the model).

Major deviations (i.e. outcome changes etc.) from this SAP will be presented/summarized in the reporting of results.

### 5.3 Specification of outcomes and timing

See appendix 1 for an overview over outcomes and timing.

- Activity engagement (measured by POES-S) at eight months follow up is the primary outcome (end point comparison)
- Personal recovery (measured by QPR), quality of life (measured by MANSA) and levels of functioning (measured by WHODAS-12) at eight months follow up are secondary outcomes (end point comparisons)
- WHODAS-36 subscales, WHODAS-36 total score and health related quality of life (EQ-5D-3L) at eight months follow up are exploratory outcomes (end point comparison).

### 5.4 Analysis methods

The trial is analyzed according to the statistical principle “intention-to-treat”. This means that analyses are based on all included participants as opposed to “per protocol” analyses.

For the primary outcomes in both trials, the null hypothesis tested is that there is no difference in activity engagement between the two groups (intervention group and control group) at 8 months’ follow-up. The null hypotheses are similar in the other analyses assuming no differences between groups.

#### 5.4.1 Baseline variables

The chi test is used to test for differences in nominal baseline variables (sex, education, housing status, marital status, diagnosis, employment status) and the t-test is used to test for differences in ordinal/continuous baseline variables (age, activity engagement, functioning, personal recovery, quality of

life). If the test assumptions in the latter are not met, a non-parametric test will be performed instead (e.g. Kruskal Wallis or Mann Whitney U test).

#### 5.4.2 Self-reported outcomes

Primary, secondary and exploratory outcomes are calculated and presented in means of scores at 8 months follow-up. In the protocol we wrote:

“The main outcome measure is activity engagement, measured by POES-S. To test the research hypothesis, the differences between the intervention group and the control group will be analyzed using ANOVA to determine the statistical significance. Effect sizes to judge clinical relevance will be calculated by Cohen’s d. In accordance with the intention-to-treat principles,

“multiple multivariate imputations” will be used and all co-variates of supposed prognostic significance will be used to impute a distribution of missing data.

The continuous power measurements will be analyzed with a repeated measurement model in mixed model analyses with unstructured variance. The prerequisite for using this analysis and for the use of multiple imputations is that data are missing at random or data missing completely at random as opposed to non-ignorable nonresponse. This distinction is important as repeated measurements and multiple imputations are both models based on a statistical estimation of non-existent responses, and the prerequisites for this estimation must be met for the analyses to be valid.” ([name] et al, 2020)

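### MA&R is partly delivered in groups, in one arm only, and no planned analysis checks the independence assumed by the primary test and the 80% power

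*SAP*

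**What the plan says.** Section 3.1 describes individual 1:1 allocation to MA&R plus usual care or to usual care alone. MA&R "consists of 11 group sessions and 11 one-to-one sessions", is led by a peer worker and an occupational therapist, and works partly through interaction between participants: "MA&R utilized various methods such as didactic presentations, peer exchange, direct experiences with activities and personal exploration". Participants came from "one of three community mental health centers in Mental Health Center Copenhagen, or were citizens in the municipalities of Copenhagen, Svendborg or Odense".

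Section 5.4.2 gives the primary test: "the differences between the intervention group and the control group will be analyzed using ANOVA to determine the statistical significance". It also plans a mixed model for repeated measurements with unstructured variance. Under section 5.5 the primary analysis adjusts only for stratification variables, and section 3.2 names one: "The randomization is stratified by sex".

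Section 5.5 lists three sensitivity analyses: adjustment for baseline characteristics that differ between the arms (site is a candidate), worst-case and best-case imputation, and the observed data.

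On size, section 3.3 says: "To achieve a statistical power of 80% and a significance level of 5%, a total of 128 participants must be included in this study". Its inputs are a difference of 3 points and an SD of 6. No ICC, group size or design effect appears.

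**The concern.** Participants who attend the same MA&R group share facilitators, fellow members and sessions. Their POES-S scores at follow-up may therefore resemble each other more than scores from different groups. This correlation can arise in one arm only, because controls have no MA&R group.

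None of the planned methods allows for it. The ANOVA assumes independent observations. The unstructured variance in the mixed model covers correlation within a participant over time, not between participants. Site in section 5.5 does not fill the gap either: it enters only if the arms look unbalanced, it is common to both arms, and it does not identify groups within a site.

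With a positive ICC, the 95% confidence interval for the primary outcome is too narrow and the 5% test rejects too often. Section 5.4.2 discusses the missing-data assumption at some length but does not mention independence, so a reader could not tell whether the primary result depends on it.

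**Working it through.** **Inputs from the SAP.** Two-sided alpha 0.05 (sections 3.3 and 5.1); difference 3, SD 6, 64 per arm (section 3.3); groups in the MA&R arm only (section 3.1).

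**Assumptions, because the SAP gives no values.** Group size m = 4, 8 or 12; ICC = 0, 0.01, 0.05 or 0.10; total SD 6 in both arms.

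**Step 1: the plan's own figure.** The standard error under independence is 6 × √(2/64) = 1.061, so the noncentrality is 3/1.061 = 2.83. The noncentral t distribution with 126 df gives power 80.1% at 64 per arm and 79.5% at 63. So 128 is exactly the answer for independent observations and contains no allowance for clustering.

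**Step 2: clustering in one arm.**
- Design effect in the MA&R arm: deff = 1 + (m − 1) × ICC
- True over assumed standard error: r = √((deff + 1)/2)
- True type I error of the nominal 5% test: 2 × (1 − Φ(1.96/r))
- Power with a correct standard error: noncentral t, 126 df, noncentrality 2.83/r

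Example, m = 8 and ICC 0.05: deff = 1.35; r = √(2.35/2) = 1.084; 1.96/1.084 = 1.808; type I error 7.06%; noncentrality 2.83/1.084 = 2.61; power 73.5%.

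| ICC | Type I error, m = 4 / 8 / 12 | Power, m = 4 / 8 / 12 |
|---|---|---|
| 0 | 5.0% | 80.1% |
| 0.01 | 5.17 / 5.40 / 5.64% | 79.6 / 78.8 / 78.0% |
| 0.05 | 5.87 / 7.06 / 8.26% | 77.3 / 73.5 / 70.0% |
| 0.10 | 6.76 / 9.16 / 11.54% | 74.5 / 67.6 / 61.6% |

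Simulation of the unadjusted test (40,000 runs per cell, m = 8) gave type I error 5.0%, 5.3%, 7.0% and 9.2% at ICC 0, 0.01, 0.05 and 0.10, in line with the formula. The power column is somewhat optimistic, since few groups leave fewer degrees of freedom than 126.

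**Step 3: how a nested analysis behaves.** Simulation with 8 groups of 8, no site effect, and the same model with and without a random intercept for group:
- ICC 0.05: type I error 0.068 without and 0.043 with; mean interval width 4.18 and 4.81 points.
- ICC 0: type I error 0.040 with; mean width 4.19 without and 4.50 with.

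Simulation with 6 assumed sites (three centers and three municipalities), site ICC 0.05, 8 groups of 8, and site as a fixed effect in the nested model (20,000 runs per cell):

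| Group ICC | ANOVA: type I error, power, width | Nested: type I error, power, width | Group variance estimated as zero |
|---|---|---|---|
| 0 | 0.050, 80%, 4.17 | 0.036, 73%, 4.65 | 57% of runs |
| 0.05 | 0.070, 79%, 4.17 | 0.043, 66%, 5.01 | 40% of runs |

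At a true group ICC of 0.05, the 5th to 95th percentiles of the estimated ICC are 0 to 0.26. Leaving site out at group ICC 0 raises the mean estimated ICC from 0.037 to 0.058, because site differences are then counted as group variance. With 6 groups, one per site, group variance cannot be told apart from an arm-by-site difference: about 5 df remain, and at ICC 0.05 the width is 5.74 against 4.16 for ANOVA and power is 55%.

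**The case against.** The strongest reply is that this is an omission and not a misstatement. Nothing in the SAP contradicts itself here, and 128 is right for its inputs. Group size and ICC are both assumed, so the effect runs from none to a type I error of 11.5%. Section 3.1 makes half the sessions one-to-one and section 5.2 says "each MA&R course is tailored to each participant", which points to the low end. At ICC 0.01 the correct standard error is only 0.7-2.7% larger than the assumed one.

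The remedy is also weak. With 8 groups, the group variance is often estimated as zero even when it is not, and the two models then coincide and may falsely reassure. Without any clustering, the nested interval with site is about 11.5% wider than the ANOVA interval (4.65/4.17), more than the 8.4% understatement at ICC 0.05 and m = 8 that it is meant to reveal. Since section 3.1 says "The enrollment started at September 2018 and lasted to August 2020", the power point can no longer change the design.

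Most of this stands, and it is why the primary analysis should not be replaced and why the point is minor. It does not remove the point: the planned standard error is too small under any positive ICC, and the SAP offers no way to learn which case applies. Part of the extra width comes from site and arm-specific variance. When the two models differ only in the group intercept and there is no site effect, the widening at ICC 0 is 7.4% (4.50/4.19), and at ICC 0.05 the type I error comes back from 0.068 to 0.043.

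**Conclusion.** The point holds, at minor severity. It is certain that the primary test, the mixed model and the sample size assume independence, and that no listed analysis examines it. How far this distorts the result is not known. Given groups of 4 to 12, clustering in the MA&R arm only and 64 per arm, the distortion is nil at ICC 0, slight at 0.01, and material from about 0.05 upward (type I error 5.9-8.3%, power 70.0-77.3%). These figures take complete data, so they show the effect of clustering alone.

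**What to change.** Keep the planned primary analysis. Add to section 5.5 one prespecified sensitivity analysis for POES-S:

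- A partially nested mixed model with arm, sex and site as fixed effects and a random intercept for the allocated MA&R group in the intervention arm only. Controls and participants never placed in a group enter as singletons. Site is there so that differences shared by both arms are not read as group variance.
- Arm-specific residual variance; REML on the observed data; Satterthwaite or Kenward-Roger degrees of freedom.
- The same model without the group intercept beside it, so that the two differ only in clustering.
- A definition of group fixed in advance, in case groups were open to later entrants.
- The ICC with a confidence interval, and the number and size of groups. Judge by the change in estimate and interval, not by significance.

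Add to section 3.3 that 128 participants give 80% power only under independence. If group membership cannot be recovered, state independence as an untested assumption.

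**Cost.** A few lines of text, a pair of model fits and no new outcome data. Group membership must be recovered from session records. Section 5.2 already plans to report group attendance, but whether the records identify the group needs checking. The nested interval will be wider and mildly conservative even without clustering, and the ICC imprecise. With only one group per site, the comparison would say little about groups as such. The text should state these limits.
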